4.4.1.2 Statistical Hypothesis, Model, and Method of Analysis

The dermatologist signs and symptoms of cutaneous irritation total score will be calculated as the sum of the individual dermal response attributes (erythema, dryness, scaling, and edema). The change from baseline in the total score will be summarised by number and percentage of subjects by visit for each product group (PPD [redacted]). Additionally the change from baseline score greater than 1 will be summarised by number and percentage of subjects by visit for each product group. No formal statistical inference will be performed.

The individual attribute responses, total score and change from baseline in total score will be listed for each subject by visit and by product group (PPD [redacted]).

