12.2.6 Primary Analysis(es)

The primary endpoint will be the change from baseline (prior to any product application) in dermatologist signs and symptoms of cutaneous irritation total score following 21 (+2) days of product use. The primary analysis will be performed using the Safety population.

The dermatologist assessment of signs and symptoms of cutaneous irritation total score will be calculated as the sum of the individual dermal response attributes (erythema, dryness, scaling, and edema). The change from baseline in the total score will be summarised by number and percentage of subjects by visit for each treatment group. No formal statistical inference will be performed.

In addition, the individual attribute responses and the total score will be listed for each subject by visit and by treatment group.

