4.4 Analysis of Tolerability

4.4.1 Primary Tolerability Endpoint

4.4.1.1 Primary Tolerability Endpoint Definition

The primary endpoint will be the change from baseline (prior to any product application) in dermatologist signs and symptoms of cutaneous irritation total score following 21 (+2) days of product use.

This study will be considered a success if at least 90% of completed subjects do not have a significant increase (i.e. a unit increase score of 1 in the total score) from baseline in dermatologist assessed signs and symptoms of cutaneous irritation following 21 (+2) days of investigational product use.

Calculation of dermatologist assessment of signs and symptoms of cutaneous irritation total score and change from baseline in total score:

The cutaneous irritation total score will be calculated in the following way:

Cutaneous irritation total score = dermal response score of erythema + dermal response score of dryness + dermal response score of scaling + dermal response score of edema

Where, the dermal response score is described in [Table 4-1](#).

Table 4-1 Dermatological Evaluation

Attribute	Description (Score)				
Erythema	None (0)	Very Slight (0.5)	Slight (1)	Moderate (2)	Severe (3)
Dryness	None (0)	Very Slight (0.5)	Slight (1)	Moderate (2)	Severe (3)
Scaling	None (0)	Very Slight (0.5)	Slight (1)	Moderate (2)	Severe (3)
Edema	None (0)	Very Slight (0.5)	Slight (1)	Moderate (2)	Severe (3)

For example, if the dermal responses score of erythema = 2, dermal responses score of dryness = 0.5, dermal responses score of scaling = 1 and dermal responses score of edema = 0.5.

Then the cutaneous irritation total score will be:

$$\text{Total score} = 2 + 0.5 + 1 + 0.5 = 4.$$

Change from baseline in dermatologist signs and symptoms of cutaneous irritation total score = total score at day 21 – total score at baseline.

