4.7 Analysis of Other Variables

No other analyses will be performed for this study.

5 Changes to the Protocol Defined Statistical Analysis Plan

Any changes from the originally planned statistical analysis specified in the protocol are outlined in [Table 5-1](#).

Table 5-1 Changes to Protocol Defined Analysis Plan

Protocol	Reporting & Analysis Plan	
Statistical Analysis section	Statistical Analysis Plan	Rationale for Changes

 • Section 6.8: Medication/treatments taken within 30 days of signing the informed consent form will be documented as a prior [redacted] medication/treatment. Medications/treatments taken after signing the informed consent form will be documented as concomitant medication/treatments. 	
 • The current standard definition of the prior medication and concomitant medications has been used in the Reporting and Analysis plan: Prior medications are defined as those which stopped before the first application of the study product. Concomitant medications are defined as the medication ongoing or started on or after the first application of the study product. 	
 • To maintain the current standard definition of prior medication and concomitant medications • Importantly, all medications/therapies concomitant to study participation will be provided. • For this study, signing the informed consent form and the first application of the study product will be on the same day. Thus, the variance in definitions will not impact the overall analysis of the prior and concomitant medications.

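### The only threshold summary of the primary endpoint counts rises greater than 1, but the 90% success rule already treats a rise of 1 as significant

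*SAP*

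**What the plan says.** SAP 4.4.1.1 states the decision criterion: "This study will be considered a success if at least 90% of completed subjects do not have a significant increase". It explains a significant increase as "a unit increase score of 1 in the total score". Protocol Section 3 has the same rule with the same definition, and applies it to investigational-product use over 21 (+2) days.

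SAP 4.4.1.2 plans three descriptive outputs for this endpoint:

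- a frequency summary: "The change from baseline in the total score will be summarised by number and percentage of subjects by visit for each product group";
- a threshold summary: "Additionally the change from baseline score greater than 1 will be summarised by number and percentage of subjects by visit for each product group";
- a listing: "The individual attribute responses, total score and change from baseline in total score will be listed for each subject by visit".

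There is no formal inference. Protocol 12.2.6 has the frequency summary ("The change from baseline in the total score will be summarised by number and percentage of subjects by visit for each treatment group") but no threshold row. SAP Section 5 says "Any changes from the originally planned statistical analysis specified in the protocol are outlined in" Table 5-1. That table covers only the definitions of prior and concomitant medication. SAP 4.5.1 uses the same cut, greater than 1, for the ocular total score.

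**The concern.** The rule and the table use the same number with different inequalities. A subject who worsens by exactly 1.0 has a significant increase under the rule but does not appear in the threshold row. On a continuous scale this would hardly matter. On a score with 0.5 steps it removes a whole score level, the one at the rule's boundary.

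The 90% rule is the trial's only stated decision criterion. With no formal inference, the count itself is the decision. The threshold row comes straight after the rule, uses the rule's number and is the only dichotomy of the endpoint, so a reader of the study report could easily take it for the success result. Used that way, it can only understate failures.

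**Working it through.** **Inputs**

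- Attribute scores are 0, 0.5, 1, 2 or 3 for erythema, dryness, scaling and edema. The total is their sum, and change is day 21 minus baseline (SAP 4.4.1.1).
- Eligible baselines are 0.5, 1 or 2 for erythema and for dryness, and 0 or 0.5 for scaling and for edema (Protocol 5.2 and 5.3).
- The plan randomizes 90 subjects so that at least 30 per arm complete (SAP 1.4). This number follows a guideline minimum, so there is no power calculation to reproduce.
- The SAP's own scoring example checks: 2 + 0.5 + 1 + 0.5 = 4.

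**Step 1. What the cut greater than 1 means.** Crossing all eligible baselines with all day-21 grades gives changes from -5 to +11 in steps of 0.5. The first value above 1 is therefore +1.5.

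**Step 2. Is exactly +1.0 easy to reach?** There are 3 × 3 × 2 × 2 = 36 eligible baselines.

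- Two half-step rises (0 to 0.5, or 0.5 to 1) give +1.0 from all 36, because scaling and edema can each always rise by 0.5.
- A single one-grade rise (1 to 2, or 2 to 3) in erythema or dryness gives +1.0 from 32. The 4 exceptions have erythema and dryness both at 0.5.

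**Step 3. The rule as counts.**

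- 30 completers: 0.9 × 30 = 27 needed, so 3 failures are allowed (27/30 = 90.0%, 26/30 = 86.7%).
- 45 completers (everyone completes; equal allocation is my assumption): 0.9 × 45 = 40.5, so 41 are needed and 4 failures are allowed (41/45 = 91.1%, 40/45 = 88.9%).

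**Step 4. Cases where the verdict flips, n = 30.**

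| Subjects above +1 | Subjects at exactly +1.0 | Free of increase, cut >1 | Free of increase, rule (≥1) |
|---|---|---|---|
| 3 | 1 | 27/30 = 90.0%, met | 26/30 = 86.7%, not met |
| 0 | 4 | 30/30 = 100%, met | 26/30 = 86.7%, not met |

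**Step 5. How often it could matter.** The documents give no event rates, so these are assumptions: a true rate p of rises of 1 or more, with 30% to 70% of those rises at exactly +1.0. The chance of meeting 90% is P(X ≤ 3) for X ~ Binomial(30, p), or P(X ≤ 4) for X ~ Binomial(45, p). For the cut >1, p is replaced by 0.7p (30% at +1.0) down to 0.3p (70% at +1.0).

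| p | n = 30, rule | n = 30, cut >1 | n = 45, rule | n = 45, cut >1 |
|---|---|---|---|---|
| 5% | 93.9% | 98.0–99.9% | 92.7% | 98.0–99.9% |
| 10% | 64.7% | 84.5–98.8% | 52.7% | 79.5–98.9% |
| 15% | 32.2% | 61.2–95.6% | 17.5% | 48.3–94.9% |
| 20% | 12.3% | 37.9–89.7% | 3.8% | 22.6–86.9% |

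**Step 6. Population.** The rule concerns completed subjects on the investigational product. The threshold row is produced for each product group, so that product has its own figure, but in the Safety population. Missing values are not imputed. The two could still differ through the percentage denominator, or through final assessments of subjects who stop early.

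**The case against.** The strongest reply is that the harm depends on a use the SAP does not prescribe. The threshold row is introduced as an addition to the frequency summary and is not tied to the 90% rule, which is stated correctly one subsection earlier. Subjects at +1.0 are not lost. The listing shows every change score, and the frequency summary shows them too if it is tabulated by value. This stands: the defect lies in what is pre-specified and how it is presented, not in the data.

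Three further points have some force.

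- Adding a descriptive row may be detail that the protocol leaves to the analysis plan, so its absence from Table 5-1 is weak evidence of a fault. It shows only that the documents give no reason for the different cut.
- The table references are redacted and no layouts are visible, so one can say only that the SAP text names no output for the rule's figure.
- The probabilities in Step 5 rest on assumed rates and span wide ranges. The count examples in Step 4 need no such assumption.

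The rule's wording is also loose, since it does not say at least 1. But a subject at +1.0 has a significant increase whether it is read as exactly 1 or as 1 or more. Only a reading of more than 1 would remove the conflict, and neither document says that.

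**Conclusion.** The concern holds and should be fixed. The cut in SAP 4.4.1.2 does not match the definition in Protocol Section 3 and SAP 4.4.1.1, and it omits one full score level that can be reached from every eligible baseline. If the row is used for the success decision, the error runs only in the product's favour, and one subject can reverse the result (27/30 against 26/30).

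Under the assumptions in Step 5, the effect is small at a 5% true rate of rises of 1 or more and large from 10% upward. At 10% with 30 completers, the chance of declaring success is 64.7% by the rule and 84.5–98.8% by the row. The mismatch itself depends on no assumed rate. Its practical weight is limited because the right count can be recovered from the planned listing.

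**What to change.** Before unblinding:

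1. In SAP 4.4.1.2, change the cut from greater than 1 to greater than or equal to 1.
2. In SAP 4.4.1.1, state that a significant increase is a rise of 1 or more in the total score. Because the protocol has the same loose wording, record the clarification in Table 5-1.
3. Add one table line with n/N and percentage of completed investigational-product subjects without such an increase, and identify it as the figure for the 90% rule.
4. Optionally, align the ocular cut in SAP 4.5.1 for consistency. No success rule depends on it.

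The cost is a few words in the SAP and one table line, with no protocol amendment and no new data. The reported figure may be less favourable. If the cut is settled only after unblinding, it is open to the charge that it was chosen by result.

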4.4.2 Secondary Tolerability Variables

4.4.2.1 Secondary Tolerability Variable 1

The key secondary endpoint will be the change from baseline (prior to any product application) in the ophthalmologist signs and symptoms of ocular irritation total score following 21 (+2) days of product use.

Calculations of ocular irritation total score and change from baseline in total score:

The ocular irritation total score will be calculated in the following way:

Ocular irritation total score = ocular response score of eczema of the eyelid + ocular response score of conjunctivitis + ocular response score of follicles + ocular response score of chemosis conjunctivae

Change from baseline in ocular irritation total score = total score at day 21 – total score at baseline.

Where, the ocular response score is described in the [Table 4-2](#).

Attribute	Description (Score)				
Eczema of the eyelid	None (0)	Very Slight (0.5)	Slight (1)	Moderate (2)	Severe (3)
Conjunctivitis	None (0)	Very Slight (0.5)	Slight (1)	Moderate (2)	Severe (3)

Follicles	None (0)	Very Slight (0.5)	Slight (1)	Moderate (2)	Severe (3)
Chemosis conjunctivae	None (0)	Very Slight (0.5)	Slight (1)	Moderate (2)	Severe (3)

Table 4-2 Ophthalmological Evaluation

4.4.2.2 Secondary Tolerability Variable 2

The other secondary endpoints will be change from baseline in subject self-assessment scores of signs and symptoms of cutaneous and ocular irritation to 1 to 2 hours after first product application and following 21 (+2) days of product use.

Calculations of subject self-assessment of cutaneous irritation total score and change from baseline in total score:

Subject self-assessment of cutaneous irritation total score = redness + dryness + itching + stinging/burning + tightness

Change from baseline in subject self-assessment of cutaneous irritation total score = total score at 1 to 2 hours (and day 21) – total score at baseline

Calculations of subject self-assessment of ocular irritation total score and change from baseline in total score:

Subject self-assessment of ocular irritation total score = redness + dryness + stinging/ burning + Itching

Change from baseline in subject self-assessment of ocular irritation total score = total score at 1 to 2 hours (and day 21) – total score at baseline

Where, the subject self-assessment of cutaneous irritation score is as described in the

[Table 4-3](#), and the subject self-assessment of ocular irritation score is as described in the [Table 4-4](#).

Table 4-3 Subject Self-Assessment Scale for Sign and Symptoms of Cutaneous Irritation

Attribute	Description (Score)				
	None (0)	Very Slight (0.5)	Slight (1)	Moderate (2)	Severe (3)
Redness	None (0)	Very Slight (0.5)	Slight (1)	Moderate (2)	Severe (3)
Dryness	None (0)	Very Slight (0.5)	Slight (1)	Moderate (2)	Severe (3)
Stinging/Burning	None (0)	Very Slight (0.5)	Slight (1)	Moderate (2)	Severe (3)
Itching	None (0)	Very Slight (0.5)	Slight (1)	Moderate (2)	Severe (3)
Tightness	None (0)	Very Slight (0.5)	Slight (1)	Moderate (2)	Severe (3)

Table 4-4 Subject Self-Assessment Scale for Signs and Symptoms of Ocular Irritation

Attribute	Description (Score)				
	None (0)	Very Slight (0.5)	Slight (1)	Moderate (2)	Severe (3)
Redness	None (0)	Very Slight (0.5)	Slight (1)	Moderate (2)	Severe (3)
Dryness	None (0)	Very Slight (0.5)	Slight (1)	Moderate (2)	Severe (3)
Stinging/Burning	None (0)	Very Slight (0.5)	Slight (1)	Moderate (2)	Severe (3)
Itching	None (0)	Very Slight (0.5)	Slight (1)	Moderate (2)	Severe (3)

4.4.3 Handling of Missing Values/Censoring/Discontinuations

Missing data will not be replaced or imputed. Subjects who withdraw from the study prematurely will be included in the statistical analyses up to the point of discontinuation.

4.5 Analysis of Secondary Objectives

4.5.1 Tolerability (Secondary)

The ophthalmologist assessment of signs and symptoms of ocular irritation total score will be calculated as the sum of the individual ocular response scores (eczema of the eyelid, conjunctivitis, follicles, chemosis conjunctivae). The change from baseline in the total score will be summarised by number and percentage of subjects by visit for each product (PPD). Additionally the change from baseline score greater than 1 will be summarised by number and percentage of subjects by visit for each product. No formal statistical inference will be performed.

The individual attribute responses, total score and change from baseline in total score will be listed for each subject by visit and by product group (PPD).

The subject self-assessment on Visit 1 will be measured twice: once prior to the LAST and product application and once 1 to 2 hours after first supervised product application. Also Subject self-assessment will be measured on Day21 as well. The change from baseline in the total subject self-assessment scores for signs and symptoms of cutaneous irritation and ocular irritation score at 1 to 2 hours after first product application and following 21 (+2) days of use

will be summarized by number and percentage of subjects by visit for each product (PPD [REDACTED]).

The individual attribute responses, total score and change from baseline in total score will be listed for each subject by visit and by product group (PPD [REDACTED]).

All secondary analyses will be performed using the Safety Population.

4.5.2 Pharmacokinetic (Secondary)

Not Applicable.

4.6 Analysis of Safety

All safety data will be reported for the Safety Population as per actual product received. The safety profile of the study product will be assessed with respect to Adverse Events (AEs).

4.6.1 Adverse Events and Serious Adverse Events

All AEs will be reviewed by the Clinical Research Scientist or Designee prior to database lock and will be coded to a system organ class (SOC) and preferred term (PT) using the Medical Dictionary for Regulatory Activities (MedDRA). During this review stage, AEs will be further categorized as skin or non-skin.

Treatment emergent adverse events (TEAEs) are defined as new AEs that occur on or after the first product application. Adverse events with an onset date/time prior to the first product application will be considered as non-treatment emergent.

Treatment emergent adverse events will be summarized by the number and percentage of subjects having any AE, an adverse event in each System Organ Class, and each Preferred Term. The following summary tables and listings will be presented by product:

- Table of TEAEs by SOC and PT (PPD [REDACTED]).
- Table of TEAEs by SOC, PT and severity (PPD [REDACTED]).
- Table of TEAEs by skin/non-skin and PT (PPD [REDACTED]).
- Table of treatment emergent treatment-related AEs by SOC and PT (PPD [REDACTED]).
- Table of treatment emergent treatment-related AEs by SOC, PT and severity (PPD [REDACTED]).
- Table of treatment emergent treatment-related AEs by skin/non-skin and PT (PPD [REDACTED]).
- Table of treatment emergent treatment-related serious adverse events (SAEs) by SOC and PT (PPD [REDACTED]) [only produced if there are more than 5 treatment emergent SAEs].
- Table of treatment emergent treatment-related non-serious SAEs by SOC and PT (PPD [REDACTED]) [only produced if there are more than 5 treatment-emergent SAEs].
- Listing of all AEs (PPD [REDACTED] for all randomized subjects; PPD [REDACTED] for non-randomized subjects).

- Listing of deaths (PPD [redacted]).
- Listing of non-fatal SAEs (PPD [redacted]).
- Listing of treatment emergent AEs leading to study or product discontinuation (PPD [redacted]).
- Listing of treatment-emergent AEs classified as skin (PPD [redacted]).

In the event that there is nothing to report, a null listing will be produced.

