A sufficient number of subjects will be screened (approximately 180) to randomize 90 subjects to ensure that at least 60 subjects (30 per arm) complete the study. It is deemed that 30 subjects per arm are considered sufficient to assess the primary endpoint: dermatologist assessment of signs and symptoms of cutaneous irritation total score. The sample size for this study has been selected based on clinical considerations and to ensure compliance with the Agência Nacional de Vigilância Sanitária (ANVISA) Guideline for the Safety Evaluation of Cosmetic Products (ANVISA, 2012) which mandates an investigational product be tested on at least 30 subjects.

Schedule of Activities

The schedule of activities table provides an overview of the subject visits and study procedures.

The investigator may schedule visits (unplanned visits) in addition to those listed on the schedule of activities, in order to conduct evaluations or assessments required to protect the well-being of the subject.

Table 1-1 Schedule of Activities

| Procedure/Assessment | Screening/Baseline | Final Visit |
|--|--------------------|-------------------------|
| | Visit 1 Day 1 | Visit 2 Day 21 (+ 2) |
| Informed Consent (date and time captured) | X | |
| Demographics | X | |
| Medical History | X | |
| Medications Review | X | X |
| Inclusion/Exclusion Criteria | X | |
| Fitzpatrick Skin Type Assessment | X | |
| Subject Self-Assessment | X ^a | X |
| Clinical Assessment by Dermatologist | X | X |
| Clinical Assessment by Ophthalmologist | X | X |
| Lactic Acid Sting Test (LAST) | X | |
| Subject Eligibility for Enrollment | X | |
| Randomization | X | |
| Product and Diary Dispensing | X | |
| Supervised Product Application ^b | X | |
| Adverse Events (AEs) Review ^c | X | X |
| Product and Diary Return | X | X |
| Study Conclusion/Subject Exit from Study | | X |

a. Subject self-assessment on Visit 1 will occur twice; once prior to the LAST and product application and once 1-2 hours after first supervised product application.

b. Supervised product application should not occur until at least 30 minutes following the LAST.

c. Adverse Events (AEs) and therefore all Serious Adverse Events (SAEs) will be collected immediately after a subject provides consent to participate in the study by completing the Informed Consent Form (ICF).

Footnotes:

The diary will be used to maintain and record compliance and to capture subject comments.

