10 ADVERSE EVENT AND SERIOUS ADVERSE EVENTS

10.1 Definition of an Adverse Event (AE)

An AE is any untoward medical occurrence in a clinical study subject, temporally associated with the use of a study product including any washout or lead-in product (or medical device), whether or not considered related to the study product, including any washout or lead-in product (or medical device).

NOTE: An AE can therefore be any unfavorable and unintended sign (including an abnormal laboratory finding), symptom, or disease (new or exacerbated) temporally associated with the use of a study product including any washout or lead-in product (or medical device).

Events Meeting the AE Definition:

- Any abnormal laboratory test results (hematology, clinical chemistry, or urinalysis) or other safety assessments (e.g. ECG, radiological scans, vital sign measurements), including those that worsen from baseline, considered clinically significant in the medical and scientific judgment of the investigator (i.e., not related to progression of underlying disease).
- Exacerbation of a chronic or intermittent pre-existing condition including either an increase in frequency and/or intensity of the condition.
- New conditions detected or diagnosed after study product administration even though it may have been present before the start of the study.
- Signs, symptoms, or the clinical sequelae of a suspected drug-drug interaction.
- Signs, symptoms, or the clinical sequelae of a suspected overdose of either study product or a concomitant medication. Overdose per se will not be reported as an AE/SAE unless it is an intentional overdose taken with possible suicidal/self-harming intent. Such overdoses should be reported regardless of sequelae.
- The signs, symptoms, and/or clinical sequelae resulting from lack of efficacy will be reported as AE if they fulfill the definition of an AE. Also, "lack of efficacy" or "failure of expected pharmacological action" constitutes an AE.

Events NOT meeting the AE definition:

- Any clinically significant abnormal laboratory findings (if applicable) or other abnormal safety assessments which are associated with the underlying disease, unless judged by the investigator to be more severe than expected for the subject's condition.
- The disease/disorder being studied or expected progression, signs, or symptoms of the disease/disorder being studied, unless more severe than expected for the subject's condition.

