- Medical or surgical procedure (e.g. endoscopy, appendectomy) is not the AE. The condition that leads to the procedure is an AE (e.g. appendicitis).
- Situations where an untoward medical occurrence did not occur (social and/or convenience admission to a hospital).
- Anticipated day-to-day fluctuations of pre-existing disease(s) or condition(s) present or detected at the start of the study that do not worsen.
- Any observed response to the LAST that can be denoted according to the score of the reactions (per [Table 8-1](#)) will not be considered an adverse event. Only in the case of unusual reactions, in the opinion of the qualified dermatologist, will these reactions and the consequences observed upon evaluation be documented as AE's.

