10.3 Reporting of Adverse Events

10.3.1 Reporting Period

All AEs, and therefore all SAEs will be collected immediately after a subject provides consent to participate in the study by the completion (signature) of the ICF and until 5 days following last administration of the study product (or last procedure).

Medical occurrences that began before obtaining informed consent will be recorded in the Medical History/Current Medical Conditions section of the CRF not the AE section.

Details recorded by the subject on a diary or similar document that meet the definition of an AE must also be discussed with the subjects and transcribed in the AE section of the CRF.

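### The treatment-emergent rule has no worsening clause, so an adverse event that starts between consent and first application and intensifies on the serum can miss every by-product AE table (low priority)

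*SAP*

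**What the plan says.** SAP 4.6.1 gives the definition: "Treatment emergent adverse events (TEAEs) are defined as new AEs that occur on or after the first product application". The next sentence settles everything earlier by onset alone: "Adverse events with an onset date/time prior to the first product application will be considered as non-treatment emergent". Nothing in either document covers an event that begins before first application and gets worse afterwards.

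Protocol 10.3.1 starts AE collection at consent: "All AEs, and therefore all SAEs will be collected immediately after a subject provides consent to participate in the study". Consent, the LAST and the first application all take place at Visit 1. A footnote to the Schedule of Activities (Protocol section 1) sets the minimum gap between the last two: "Supervised product application should not occur until at least 30 minutes following the LAST".

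Protocol 10.1 counts worsening as an AE in its own right: "Exacerbation of a chronic or intermittent pre-existing condition including either an increase in frequency and/or intensity of the condition". Protocol 10.6 has new or updated information on an event entered on the AE page of the CRF. Protocol 12.2.8 asks for treatment-emergent summaries but does not define the term.

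**The concern.** A worsening clause exists to catch an event that was already there and that the product then made worse. Here every randomized woman has lactic acid applied to part of the face and, at the same visit, has a serum applied to the face. An AE already on record when the serum goes on, whether a LAST reaction or something unrelated, keeps its early onset. It therefore stays outside the treatment-emergent set however much it intensifies.

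The by-product AE tables are the summary evidence for the safety objective, and all of them are restricted to treatment-emergent events. For any given set of AE records, leaving out the clause can only hold the treatment-emergent counts level or lower them.

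**Working it through.** The documents give no AE rates and no figure to reproduce, so the check applies the rule to a case and follows it through the planned outputs.

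**1. Can such an event be on record before first application?** Yes. Collection runs from consent (Protocol 10.3.1). Any unrelated Day 1 AE qualifies. For LAST reactions the route is narrow. Protocol 10.1 lists among events that are not AEs "Any observed response to the LAST that can be denoted according to the score of the reactions" in Table 8-1. The exception follows: "Only in the case of unusual reactions, in the opinion of the qualified dermatologist, will these reactions and the consequences observed upon evaluation be documented". Those unusual reactions do enter the AE record.

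**2. How is later worsening recorded?** Protocol 10.6 points to updating the existing record. No text calls for a second record with its own onset. Protocol 10.1 would let a site enter an exacerbation as a new AE, but does not oblige it to.

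**3. How does the SAP classify it?** If the existing record is updated, onset precedes application, so the event is non-treatment emergent at any later intensity. If a new record is opened, onset follows application and the event is treatment-emergent. The same clinical course is therefore counted or not according to an unspecified data-entry choice.

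A neighbouring case shows the gap. A condition that began before consent goes to medical history (Protocol 10.3.1). Its exacerbation after application is an AE under Protocol 10.1, would ordinarily carry a post-application onset, and so would count. The same exacerbation of an event that began shortly after consent need not.

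**4. Which SAP 4.6.1 outputs would omit it?**
- Tables restricted to treatment-emergent events: 6 unconditional + 2 produced only if there are more than 5 treatment-emergent SAEs = 8, which is every AE table.
- Listings with the same restriction: 2 (AEs leading to discontinuation; skin AEs).
- Outputs that would still show it: the listing of all AEs for randomized subjects and, if serious, the listing of deaths or of non-fatal SAEs.

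The event is missing from whichever of the 8 + 2 = 10 restricted outputs it would otherwise qualify for.

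**5. Size per subject.** Planned randomization is 90. The allocation ratio is not stated; assuming equal arms, n = 90/2 = 45. One misclassified subject changes the incidence for that preferred term by 1/n = 1/45 = 0.022, or 2.2 percentage points. The any-TEAE row moves by the same amount only if she has no other treatment-emergent event.

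**6. Effect on the main result.** The primary endpoint is the change in the dermatologist total score from a pre-LAST baseline to Day 21, and the 90% success criterion is built on that score. Neither uses the treatment-emergent classification.

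**The case against.** The best case on the other side is about reach, and most of it stands.

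- **Ordinary LAST stinging is not involved.** A reader might infer that routine stinging aggravated by the serum drops out of the safety tables. It was never going to enter them: responses that fit Table 8-1 are not AEs, and neither are dermal responses that fit the 0 to 3 grading scale (Protocol 5.8 and 9.2.1). Only reactions judged unusual qualify.
- **Eligibility is confirmed after the LAST.** Some women with an unusual facial reaction may never be randomized. All of the roughly 90 randomized women pass through the window, but that is not the number at risk of misclassification.
- **Scores capture part of the same information.** Self-assessment is repeated 1-2 hours after first application, and the dermatologist scores again at Day 21, both against a baseline taken before the LAST. A gradable reaction present at those times counts against the product.
- **There is no conflict with the protocol.** A reader might see SAP 4.6.1 as contradicting Protocol 10.1. It does not: 10.1 defines an AE, and the protocol never defines treatment emergence.
- **The rule applies to both arms alike**, in a study that plans no formal inference.
- **A site may enter the worsening as a new AE**, in which case nothing is lost.

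These points make the gap small. None shows that the documents provide for the worsened event: the last relies on a practice that neither document requires.

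**Conclusion.** The point holds as a cheap, low-priority improvement. As written, an AE recorded between consent and first application that intensifies after the serum is applied is left out of all eight AE tables and of the treatment-emergent skin and discontinuation listings, unless the site chooses to record the worsening separately.

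The number of such events is likely to be very small and cannot be estimated from the documents, which give no AE rates; any count would be a guess. The per-subject effect of about 2.2 points rests on equal arms of 45.

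Two stronger conclusions are tempting and unsupported. The event does not disappear from the report, because the listing of all AEs keeps it. The study's tolerance conclusion is not biased by the rule, because neither the primary endpoint nor the success criterion depends on it.

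**What to change.** In SAP 4.6.1, define a treatment-emergent AE as one that starts, or is already present and increases in intensity, on or after the first product application. State alongside it that such an increase is recorded with its own date/time and intensity, so that the rule can be applied to the data. If the CRF can no longer be changed, the definition can still be applied at the AE review before database lock, wherever worsening was documented.

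The cost is one or two SAP sentences and a CRF field or completion instruction. The downside is that a LAST reaction that worsens of its own accord may occasionally be counted; it can be identified in the listing of all AEs.

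Two additions are optional: a rule for Day 1 AEs with a missing onset time, and a flag in the listing for AEs first seen between the LAST and first application.
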